5.2 Derived Variable

- AE duration = AE Stop Date – AE Start Date +1
- The Skin score at visit 4, 5 and 6 are positive (1+, 2+ or 3+) and visit 3 are doubtful or irritant then it will be considered as Positive (1+) at visit 3.

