6.11 T.R.U.E. TEST®

T.R.U.E. TEST®, (Thin-layer Rapid Use Epicutaneous Patch Test) was originally granted a Biologics License for 23 allergens and a blank patch (control) in 1994 (BL No. 1623). The allergens were selected from substances widely reported to induce Allergic Contact Dermatitis (ACD). As new allergens become clinically relevant in the U.S. population, there is an ever-growing need to expand the number of allergens included in T.R.U.E. TEST®. The next 5 allergens were added to a third panel of the T.R.U.E. TEST® product in 2007 (BL103738/5019 and BL 103738/5027). An additional seven allergens were added in 2012. The current U.S. available T.R.U.E. TEST® product includes three panels of 36 allergen polyester patches including a blank patch (control). Each 0.81 cm² allergen patch is coated with one specific allergen or allergen mix. The allergens/allergen mixes are incorporated in exact dosage in a hydrophilic gel. The allergen-gel preparation is coated on an impermeable backing of polyester and dried to a thin film. The coated sheet is then cut into 9 mm x 9 mm squares (test patches), which are mounted on tape forming a standard test panel. The 3 panels together form a standard test kit. All 3 panels are typically applied to the skin of the upper back. The humidity of the skin hydrates the film and transforms to a gel, allowing the allergen to migrate into the skin, thereby reaching the cells of the immune system. The test is removed after 48 hours and read at 72-96 hours after the application, when the allergic responses are fully developed and mild irritant reactions have faded. Additional readings at 1 week and 21 days after panel placement are also advised in some cases.

Figure 1: T.R.U.E. TEST® Panel

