10.3.2 Allergic Skin Responses

Allergen site reactions will be evaluated for the presence of erythema, infiltration, papules, discrete vesicles and bullous reactions. These criteria will be used to score skin reactions according to standard patch testing guidelines established by the International Contact Dermatitis Research Group as discussed and shown below.

Skin reactions at test sites will be scored as: (Neg) negative; (IR) irritant reaction; (?) doubtful reaction; (1+) weak positive reaction; (2+) strong positive reaction; or (3+) extreme positive reaction.

Figure 6: Reaction Criteria

Notation Description Interpretation

Neg	Negative, no skin changes in the tested area,
?+	Faint, non-palpable erythema, possibly few papules
+(1+)	Palpable erythema, moderate edema or infiltrate, possibly few papules, no vesicles. Weak reaction.
++ (2+)	Strong infiltrate, numerous papules, possibly few vesicles present. Strong reaction.
+++ (3+)	Coalescing vesicles, bullae or ulceration. Extreme reaction.
IR	Inflammation sharply limited to the exposed area, lack of infiltrate, small petechiae, pustules, and efflorescences other than papules and vesicles.

Subject-reported adverse events, worsening of a pre-existing condition/disease/symptom or changes to concomitant medications will be recorded.

De-identified photographs of site reactions may be taken at the discretion of the Investigator and will not be reviewed or collected by the study sponsor.

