10.5 Visit 6: Day 19-23

The investigative site will phone the subject to determine if there are any unresolved tape, polyester chip or allergen reactions at the test sites. If the subject reports no remaining reactions, the Investigator may choose at this point to complete the visit over the telephone.

- If the visit is conducted over the telephone all visit related paperwork including adverse events and/or changes to concomitant medications will be recorded.

Should the Investigator elect to see the subject in the office, the following procedures will be performed:

- Unresolved tape and or polyester chip induced irritation will be evaluated.
- Sites will be examined for the presence of erythema, infiltration, papules, discrete vesicles and bullous reactions and scored as follows: (-) negative, (1+) weak positive reaction, (2+) strong positive reaction, and (3+) extreme positive reaction.
- All reactions (scores of 1+, 2+ or 3+) will be categorized as either late or persistent. Late reactions are defined as reactions that initially occur at 7-10 days after application of the panels. Persistent reactions are defined as reactions that appear at day 2-4 and persist through day 7-21. Persistent reactions will be clarified as either persistent-healing or persistent-escalating. If a persistent-escalating reaction is noted at Visit 6, the investigator will determine required follow up action.
- Subject-reported adverse events, worsening of a pre-existing condition/disease/symptom or changes to concomitant medications will be recorded.
- De-identified photographs of site reactions may be taken at the discretion of the Investigator and will not be reviewed or collected by the study sponsor.

10.6 Post Visit 6

The Investigator will:

1. Evaluate tape or polyester chip induced irritation that increased in severity or persisted beyond visit 3. A potential allergic response may be considered if the skin response is consistent with criteria used to score 1+, 2+ or 3+ positive skin reactions according to standard patch testing guidelines established by the International Contact Dermatitis Research Group. The skin reaction must present with:
 - Palpable erythema, moderate edema or infiltrate, possibly few papules, no vesicles. Weak reaction (Score of 1+).
 - Strong infiltrate, numerous papules, possibly few vesicles present. Strong reaction (Score of 2+).
 - Coalescing vesicles, bullae or ulceration. Extreme reaction (Score of 3+).

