2. Categorize the skin reactions at each site as either negative or positive. No skin reaction scores (1+, 2+ or 3+) assigned to during any of the reaction assessment visits, (Visits 3-6) would constitute a negative reaction. A positive skin reaction is defined as an assigned score of 1+, +2 or 3+ during at least one of the reaction assessment visits (Visits 3-6).

[figure not shown]

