3.5 Change to Analysis from Protocol

There is no change in analysis from protocol for this study.

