4.2 Secondary Endpoint (Safety)

Determination of allergen safety:

- Frequency of tape and polyester chip induced irritation or allergic reactions at Visits 2 through 6.
- Frequency of subject reported sensations of itching and/or burning for each allergen panel at patch removal.
- Frequency of positive (1+, 2+, 3+) skin reactions for each investigational and reference allergen dose at each post removal visit and overall.

STATISTICAL ANALYSIS PLAN

Date : 30 NOV 19

Version: 01

Product Name:

Sponsor Study No.: SP 14 8MP 201 Metal Allergen Epicutaneous Patch

- Frequency of negative, doubtful, irritant, late and persistent skin responses for each investigational and reference allergen dose at each post removal visit (late and persistent reactions at visits 4, 5 and 6 only).
- Frequency of all adverse events. Documentation for all local and systemic adverse reactions classified by the investigator as possibly or definitely related to the study product (e.g., erythema, hyperpigmentation, hypo-pigmentation, skin thinning or dermatitis flare) will include grade (mild, moderate or severe) and time point (clinic visit).

5. Statistical Considerations

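### SAP 5.2 recodes a recorded doubtful or irritant Visit 3 score to 1+ from later visits; the protocol has no such rule and SAP 3.5 declares no change

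*SAP*

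**What the plan says.** SAP 5.2 (Derived Variable) has a rule that looks back from later visits. If the skin scores at Visits 4, 5 and 6 are positive and those at "visit 3 are doubtful or irritant then it will be considered as Positive (1+) at visit 3".

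SAP 3.5 states: "There is no change in analysis from protocol for this study".

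Protocol 10.3.2, Figure 6, defines the Visit 3 grades by what is seen and felt. Doubtful (?+) is "Faint, non-palpable erythema, possibly few papules". Irritant (IR) is "Inflammation sharply limited to the exposed area, lack of infiltrate", with further features. Weak positive (1+) requires palpable erythema.

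Protocol 10.6 then sets the overall category for a site: "A positive skin reaction is defined as an assigned score of 1+, +2 or 3+ during at least one of the reaction assessment visits", meaning Visits 3 to 6.

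SAP 4.2 makes the visit-level grades an endpoint: "Frequency of negative, doubtful, irritant, late and persistent skin responses for each investigational and reference allergen dose at each post removal visit". Another item in SAP 4.2 asks for the positive frequencies by visit and overall. Protocol 7.2 requires the same.

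**The concern.** The recode replaces a recorded Visit 3 grade with one the investigator did not assign, using readings taken between Day 7 and Day 23. Nothing in the protocol's scoring sections (10.3 to 10.6) or analysis sections (4.15, 7.2, 12.1) provides for this.

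Visit 3 falls on Day 3-4, which is 3 × 24 = 72 to 4 × 24 = 96 hours. Protocol 6.11 describes the existing product as "read at 72-96 hours after the application, when the allergic responses are fully developed and mild irritant reactions have faded". A Visit 3 table is therefore naturally read as showing what was seen at that reading. After the recode it no longer does, and the change runs one way: positives can only rise, and doubtful and irritant can only fall. Irritancy is a safety measure here. A reader who relies on SAP 3.5 would not know that the scores had been altered.

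The trigger is also loosely worded. Naming Visits 4, 5 and 6 most plainly means all three, but the text does not exclude any one of them. Visit 6 may also have no score, since "If the subject reports no remaining reactions, the Investigator may choose at this point to complete the visit over the telephone", and SAP 5.2 does not mention that case.

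**Working it through.** The plan states no figure for this rule, so there is none to reproduce. The check has three parts.

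**1. Is there a protocol source for the rule?**

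| Place | Treatment of a Visit 3 doubtful or irritant score |
|---|---|
| Protocol 10.3.2, Figure 6 | Separate grades, distinct from 1+ |
| Protocol 10.6 | Overall positive status from assigned scores at Visits 3-6; no back-dating |
| Protocol 4.15, 7.2, 12.1 | Doubtful and irritant tabulated as such |
| SAP 5.2 | Becomes 1+ if Visits 4, 5 and 6 are positive |
| SAP 3.5 | Declares no change |

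The rule is new in the SAP, and SAP 3.5 does not declare it.

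**2. Which results can change?** Enumerate every score path for one site. Visit 3 has six grades (Neg, ?, IR, 1+, 2+, 3+). Visits 4 to 6 have the four grades listed in Protocol 10.4.2 and 10.5 (negative, 1+, 2+, 3+). That gives 6 × 4³ = 384 paths.

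- All three later visits positive: 2 × 3³ = 54 paths trigger the recode.
- Any one later visit positive: 2 × (4³ − 1) = 126 paths trigger it.

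| Result after the recode | All three (54) | Any one (126) |
|---|---|---|
| Visit 3 grade becomes 1+ | 54 | 126 |
| Any-visit positive status changes | 0 | 0 |
| Highest grade changes | 0 | 0 |
| Late becomes persistent, if derived from recoded scores | 54 | 120 |
| Site scored only 3+ later gains a 1+ | 2 | 14 |

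The 120 is 2 × (64 − 4): it leaves out the paths whose first positive is at Visit 6. The 2 is 2 × 1³, and the 14 is 2 × (2³ − 1). These are counts of logical patterns, not expected frequencies.

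A triggered site is already positive at a later visit, so the any-visit count of 15 subjects cannot move. Kappa does not move either if it uses the Investigator Determination named in SAP 6.1, which is the any-visit category.

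**3. How large is the Visit 3 shift?** If k subjects are recoded among n tested at a dose, Visit 3 positives rise by 100 × k/n percentage points, and doubtful plus irritant fall by the same amount. The documents give neither k nor n per dose. The values below are assumptions; 400 is the overall cap on subjects in Protocol 12.2.

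| n | k = 1 | k = 3 | k = 5 |
|---|---|---|---|
| 100 | 1.00 | 3.00 | 5.00 |
| 200 | 0.50 | 1.50 | 2.50 |
| 400 | 0.25 | 0.75 | 1.25 |

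**The case against.** The strongest reply is that little depends on this. The affected counts are descriptive, carry no test or decision rule, and leave the main primary count alone. The rule is set in a SAP that is to be final before database lock and that says its methods supersede the protocol's statistical section. A doubtful reaction that later stays positive was plausibly allergic from the start. All of this supports a moderate rating. It does not make SAP 3.5 true, and it does not justify overwriting the observation: the any-visit definition already counts such a site as positive, so the recode adds nothing there.

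Several narrower replies have force:

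- **Telephone Visit 6.** The call replaces the visit only when no reaction is reported, and SAP 5.6 does not impute missing data. On the all-three reading such a site is simply not recoded. What remains open is the all-or-any wording and the lack of an explicit statement.
- **Unequal treatment of similar sites.** Two sites with identical scores at Visits 3 to 5 can get different Visit 3 results, depending on whether the reaction has healed by Day 19-23. Any rule that requires sustained positivity does this. It is odd for a Visit 3 result, but it is not a contradiction.
- **Late and persistent.** The protocol has these categories assigned at the visits, and no SAP text derives them from scores. The reclassification is therefore conditional. If the investigator's category is tabulated and a site was called late, it would sit beside an analysed Visit 3 score of 1+.
- **Reading time.** Protocol 6.11 describes the existing product and also advises further readings in some cases. Protocol 8.1 explains that this study's later readings guard against missed late reactions. Those readings have their own visits in the tables, so this is no reason to alter Visit 3.
- **Size.** Both k and n are assumed. Because some subjects receive only selected panels (Protocol 10.1), n per dose may be well below 400.

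**Conclusion.** The point holds and should be fixed. SAP 5.2 adds a rule the protocol does not contain, SAP 3.5 is wrong as written, and the Visit 3 positive, doubtful and irritant frequencies shift in a fixed direction for each investigational and reference dose that has triggered sites. The true size is unknown; 0.25 to 5.00 percentage points per dose illustrates the assumed inputs and is not an expected effect.

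The any-visit count of 15 subjects shifts by 0, and so does kappa on the Investigator Determination. Two routes to dose selection remain, both conditional on how SAP 6.1 is read. The first is its instruction to repeat the procedure at all visits, if that means a separate run at Visit 3. The second is its fallback to 1+ and 2+ responses, if that counts any such grade at any visit.

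**What to change.** Delete the recode from SAP 5.2 and tabulate Visit 3 scores as recorded. If the sponsor wants to keep it:

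- show it only as a labelled sensitivity table beside the recorded scores;
- state that all three of Visits 4, 5 and 6 must be positive;
- say how a telephone or missing Visit 6 is treated;
- declare the rule in SAP 3.5.

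In either case, tabulate late and persistent reactions from the investigator's recorded categories or from unmodified scores.

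The cost is one SAP bullet removed or, if the rule is kept, a sentence in SAP 3.5, an explicit trigger and one extra table. No new data are needed.

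Two nearby text points are separate and do not bear on the rating. The late-reaction window is Day 7-14 in Protocol 10.4.2 but Day 7-10 in Protocol 10.5. The Visit 4 to 6 grade lists in those sections have no doubtful or irritant grade, although SAP 4.2 asks for those frequencies at every post-removal visit. Each pair should be reconciled.

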5.3 Site Pooling

- This section is not applicable for the study.

5.4 Reporting Precision

All outputs will be generated based on the specifications mentioned in the document of Mock TLFs.

Summary statistics will be presented to the following degree of precision:

Statistic	Degree of Precision
-----------	---------------------

STATISTICAL ANALYSIS PLAN

Date : 30 NOV 19

Version: 01

Product Name:
Sponsor Study No.: SP 14 8MP 201 Metal Allergen Epicutaneous Patch

Mean and Median	One more decimal place than the raw data
Minimum and Maximum	Same as the raw data
Standard deviation	Two more decimal places than the raw data
Percentage, ratios and CI	Two decimal places
p-value	Four decimal places or as <0.0001

Examples for the Decimal Places:

If percentage value is 0 or 100, it will be reported as '0' and '100' respectively.

Ratios and/or Confidence Interval (CI) will be reported as percentages with at least 2 decimal places (e.g. xx.xx, (xx.xx, xx.xx)).

Rounding of data will be followed as mentioned in below examples (if required):

Requirement	Original values	Rounded values
4 decimal points	0.07542	0.0754
2 decimal points	0.75462	0.75
1 decimal point	0.75462	0.8

Statistical significance will be based on two-sided hypothesis testing. P-values less than 0.05 will be considered to be significant.

5.5 Multiple Comparison/ Multiplicity

This section is not applicable for the study.

5.6 Handling of Dropout or Missing Data

Missing data will not be imputed.

Imputation of partial dates:

If medication end date is missing or partially known, the following algorithm will be used to determine if the medication is prior or concomitant:

- The latest possible date matching the partially known date will be imputed. That is, if the year and month are known, the last day of this month will be imputed; if only year is known, consider last month of that year and then the last day of the same month will be imputed.
- The medication will be considered concomitant if this imputed end date is on or after the date of the first use of the study medication (any study medication).
- If end date is unknown, the medication will be considered concomitant.

STATISTICAL ANALYSIS PLAN

Date : 30 NOV 19

Version: 01

Product Name:

Sponsor Study No.: SP 14 8MP 201 Metal Allergen Epicutaneous Patch

5.7 Interim Analysis

This section is not applicable for the study.

6. Statistical Analysis

6.1 Primary Endpoint Analysis

Primary Endpoint 01:

The lowest concentration of each dilution series allergen eliciting positive responses in a minimum of 15 subjects. Positive responses are defined as score of 1+, 2+ or 3+ during at least one reaction assessment visit. If a significant number of 3+ responses are elicited, the dose will be selected based on 1+ and 2+ responses.

The frequency and percentages of skin responses; “Negative, Irritant, Doubtful and Positive (1+, 2+, 3+)” will be calculated for each dilution series investigational allergen dose and reference allergen.

The optimal allergen dose will be based on following criteria:

1. The optimal allergen dose based on reaction scores will be based on lowest dose eliciting positive reactions.

Example:

Step#1: Subject recorded with either of score i.e. 1+, 2+, 3+ then subject's corresponding position allergen dose will be considered as “Positive Allergen Response”.

Step#2: The allergen dose from the respective dilution series eliciting positive reactions (i.e. 1+, 2+, 3+) will be considered as lowest concentration eliciting positive reactions.

This procedure will be repeated for all visits.

If a significant number of 3+ responses are elicited, the optimal allergen dose will be selected based on 1+ and 2+ positive responses.

Frequency and percentage analysis of skin reaction score will be carried out for investigational and reference allergen to obtain the optimal dosage.

Primary Endpoint 02:

For all sites with the exception of Germany (i.e. Site 6): Concordance will be measured using Cohen's kappa where less than 0% indicates no agreement, 0-20% indicates poor agreement, 20-40% indicates fair agreement, 40-60% indicates moderate agreement, 60-80% indicates good agreement and 80% or higher indicates very good agreement.

Concordance will be measured using all subjects who are tested with each allergen and corresponding reference allergen.

STATISTICAL ANALYSIS PLAN

Date : 30 NOV 19

Version: 01

Product Name:

Sponsor Study No.: SP 14 8MP 201 Metal Allergen Epicutaneous Patch

Data from all the sites by investigational allergen and corresponding Reference Allergen (RA) will be considered to assess the concordance.

Subjects with Missing Response at Investigator Determination of either panel (i.e. Investigational or respective Reference Panel) will not be considered for assessment of concordance.

Overall concordance of skin reaction responses from each allergen dose will be compared with reference allergen by using Kappa statistic as described below,

Kappa statistics (K) = $(P_0 - P_e) / (1 - P_e)$

Where P_0 is the relative observed agreement among raters (identical to accuracy), and P_e is the hypothetical probability of chance agreement and the Kappa agreement statistics score is interpreted as,

≤ 0 as indicating no agreement

0.01 – 0.20 as poor agreement

0.21 – 0.40 as fair agreement

0.41 – 0.60 as moderate agreement

0.61 – 0.80 as good agreement

0.81 – 1.00: very good agreement

Concordance will be measured using all subjects who are tested with each allergen and corresponding reference allergen.

Note: Data from the subjects with the completely detached patches for the intended wear period (approximately 48 hours or two days) will not be included in the analysis of positive responses necessary to determine optimal dose.

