7.1 Primary Endpoint

Determination of optimal test allergen dose as:

- The lowest concentration of each dilution series allergen eliciting positive responses in a minimum of 15 subjects. Positive responses are defined as score of 1+, 2+ or 3+ during at least one reaction assessment visit. If a significant number of 3+ responses are elicited, the dose will be selected based on 1+ and 2+ responses.
- For all sites with the exception of Germany: Concordance will be measured using Cohen's kappa where less than 0% indicates no agreement, 0-20% indicates poor agreement, 20-40% indicates fair agreement, 40-60% indicates moderate agreement, 60-80% indicates good agreement and 80% or higher indicates very good agreement. Concordance will be measured using all subjects who are tested with each allergen and corresponding reference allergen.

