10.4.2 Allergic Skin Responses

Allergen sites will be examined for the presence of erythema, infiltration, papules, discrete vesicles and bullous reactions and scored as follows: (-) negative, (1+) weak positive reaction, (2+) strong positive reaction, and (3+) extreme positive reaction.

All reactions (scores of 1+, 2+ or 3+) will be categorized as either late or persistent. Persistent reactions will be further clarified as either persistent-healing or persistent-escalating.

Definitions:

Late Reaction: A reaction that initially appears at day 7-14 after application of panels.

Persistent Reaction: A reaction that initially appears at day 2-4 and persists through day 7-21 or beyond.

Persistent-Healing: A persistent reaction that has not worsened since the previous evaluation, remains the same or appears to be healing.

Persistent-Escalating: A persistent reaction that has worsened since the previous evaluation

Subject-reported adverse events, worsening of a pre-existing condition/disease/symptom or changes to concomitant medications will be recorded.

De-identified photographs of site reactions may be taken at the discretion of the Investigator and will not be reviewed or collected by the study sponsor.

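### SAP 6.1 states the primary dose-selection rule in two inconsistent ways: a 15-subject, any-visit rule at the top, then a criterion and steps that omit the 15 and are repeated by visit

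*SAP*

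**What the plan says.** Protocol sections 7.1 and 12.1 and SAP section 4.1 define the optimal dose as "The lowest concentration of each dilution series allergen eliciting positive responses in a minimum of 15 subjects". A subject counts as positive with a score of 1+, 2+ or 3+ at one or more assessment visits. SAP 6.1 opens with the same rule.

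SAP 6.1 then lists what the dose will be based on. The single numbered item is "The optimal allergen dose based on reaction scores will be based on lowest dose eliciting positive reactions". An example in two steps follows. Step 1 marks a subject's dose as positive when any of the three scores is recorded. Step 2 reads "The allergen dose from the respective dilution series eliciting positive reactions (i.e. 1+, 2+, 3+) will be considered as lowest concentration eliciting positive reactions". The text continues: "This procedure will be repeated for all visits".

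Four other places bear on the reading:
- SAP section 1 says the SAP's methods supersede the protocol's statistical section, while SAP 3.5 declares no change from the protocol.
- SAP section 7 lists only kappa for the primary endpoint, on the FAS. SAP 3.6.2 puts all efficacy analysis on the mFAS.
- Protocol 10.6 has the investigator make one positive or negative call per site, over Visits 3-6 together.
- The kappa part of SAP 6.1 already relies on such a call, since it drops "Subjects with Missing Response at Investigator Determination of either panel".

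**The concern.** This rule produces the trial's main conclusion, the dose chosen for each allergen. A programmer who follows the numbered criterion and the steps, and not the sentence above them, has no threshold to apply and is told to run the selection at each visit. That could select a lower dose on a handful of positives, or a different dose at each visit with nothing to decide between them.

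By-visit and any-visit counts will differ by design:
- A late reaction is "A reaction that initially appears at day 7-14 after application of panels", so Visit 3 cannot show it.
- At Visit 6, if the subject reports no remaining reactions, "the Investigator may choose at this point to complete the visit over the telephone".
- SAP 5.2 re-scores a doubtful or irritant Visit 3 result to 1+ when the later visits are positive. That changes a Visit 3 count but not an any-visit count, because the subject is already positive later.

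**Working it through.** **The plan's own figure.** The only numerical basis offered is in SAP 3.3: past studies had 20 subjects per allergen and a target response of 70-90%, giving a minimum of 14. Check: 0.70 × 20 = 14.0, which reproduces. The 15 itself is not derived (15/20 = 75%, inside the target range), and there is no power calculation to reproduce.

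**The two statements side by side.**

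| Element | Opening of SAP 6.1, SAP 4.1, protocol 7.1 and 12.1 | SAP 6.1 criterion 1 and steps |
|---|---|---|
| Minimum positives at the dose | 15 subjects | none stated |
| Visits | positive at any visit | procedure repeated at each visit |
| Combining visits | built into the definition | none stated |

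**How far the readings can diverge.** The documents give no positivity rates, so every rate here is an assumption. Subjects are treated as independent.

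*No minimum against 15.* With N tested and true positivity p at the dose, P(at least 1) = 1 − (1 − p)^N, and P(at least 15) is the upper binomial tail P(Bin(N, p) ≥ 15).

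| p | N | P(at least 1) | P(at least 15) |
|---|---|---|---|
| 1% | 100 | 0.634 | 1.1 × 10⁻¹³ |
| 1% | 200 | 0.866 | 2.6 × 10⁻⁹ |
| 1% | 400 | 0.982 | 1.7 × 10⁻⁵ |
| 2% | 400 | 0.9997 | 0.016 |
| 3.75% | 400 | about 1 | 0.536 |
| 5% | 400 | about 1 | 0.901 |

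The two readings part most sharply at low positivity. At 5% of 400 they mostly agree.

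*One visit against any visit.* Suppose a dose has 18 any-visit positives and so qualifies. If each is scored positive at a given visit with probability v, that visit alone reaches 15 with probability P(Bin(18, v) ≥ 15).

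| v | 18 any-visit positives | 20 any-visit positives |
|---|---|---|
| 0.9 | 0.902 | 0.989 |
| 0.8 | 0.501 | 0.804 |
| 0.7 | 0.165 | 0.416 |
| 0.6 | 0.033 | 0.126 |

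**What 15 positives represent (for the optional table).** Exact 95% limits for 15/N are the 0.025 quantile of Beta(15, N − 14) and the 0.975 quantile of Beta(16, N − 15).

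| N tested | Proportion | Exact 95% CI |
|---|---|---|
| 100 | 15% | 8.65-23.53% |
| 200 | 7.5% | 4.26-12.07% |
| 300 | 5% | 2.83-8.11% |
| 400 | 3.75% | 2.11-6.11% |

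The number tested per metal is not fixed, because protocol 10.1 lets the investigator restrict a past-positive subject to some panels. The 400 is a ceiling for the whole study.

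**The case against.** The strongest defence is that the 15-subject rule stands a few lines above the criterion and again in SAP 4.1, and SAP 3.5 declares no change. The steps are only an example. Step 1 is written per subject, so Step 2 may mean each subject's own lowest eliciting concentration. Repeating the procedure at all visits may mean no more than searching every visit for a positive, which an any-visit rule requires. This stands as far as it goes: a reader might infer that the 15 was abandoned and that one positive suffices, and the documents do not support that. The defence does not remove the inconsistency, because criterion 1 is not part of the example and lacks the 15, and Step 2 sits inside the repeated procedure.

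Other stronger readings also fail:
- *Missing intervals and control rates are an error.* SAP 6.1 already plans frequencies and percentages for each dose, and the table shells are in a separate document not available here. An interval would not change which dose a count rule selects.
- *Kappa lacks a cut-off by oversight.* Amendment III replaced a requirement for moderate to very good concordance with wording that only measures it, so the absence looks deliberate.
- *The completion quota should guarantee a qualifying dose.* The quota also counts subjects positive only to a reference. No section claims that meeting it yields 15 at one dose, and protocol 4.10 lets the study end at 400 subjects with the quota unmet.

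**Conclusion.** The point holds as an internal inconsistency in the primary analysis section, and should be fixed. SAP 6.1 gives two rules that can select different doses. Section 7 does not arbitrate, since it omits the count rule. Pointing to the protocol is not a safe default either, because the SAP says it supersedes the protocol's statistical section.

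The textual finding rests on no assumption. The probabilities do: they use assumed rates, apply only if the criterion and steps are followed literally, and show that the choice of reading could matter, not that it will.

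**What to change.** Required, in the SAP, before it is finalised ahead of database lock and before the randomization key goes to data management (after that, choosing a reading would be post hoc):
- In 6.1, write the minimum of 15 subjects, each counted once, into criterion 1 and Step 2.
- Replace the visit loop with one classification per subject and dose, consistent with protocol 10.6: positive if scored 1+, 2+ or 3+ at one or more of Visits 3-6; negative if assessed with no such score; missing if there is no usable reading. Without the third category, unread subjects would become negatives, although SAP 5.6 rules out imputation.
- Keep by-visit frequencies as descriptive tables.
- Add the count rule to the primary row of section 7, reconcile FAS with mFAS, and keep the exclusion of completely detached patches.

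Optional:
- Report n/N per dose among evaluable subjects tested with that allergen, with an exact 95% CI, and show positives on the blank, PVP and HPC patches beside it. The downside is extra tabulation and wide intervals.
- State in one sentence whether kappa is descriptive.

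The required part costs a few lines of SAP text. The optional tables use data already collected. Neither needs a protocol amendment or more subjects, and the required change restores the protocol's own count rule.
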